3. PARTICIPANT SELECTION

3.1 Eligibility Criteria

All screening assessments must be completed within 42 days prior to the date of treatment initiation.

3.2 Inclusion Criteria

- Histologically confirmed adenocarcinoma of the prostate
- Castration-resistant prostate cancer requires the following 3 criteria:
 - Progression after surgical castration or on GnRH agonist or antagonist
 - A castrate level of testosterone (<50ng/dL)
 - Prostate cancer progression documented by PSA rise or bone progression according to PCWG2²³
- There is no limit to number of prior therapies
- Metastatic disease by bone scan
- Age ≥ 18 years

- Eastern Cooperative Oncology Group (ECOG) performance status of 0 or 1 (Appendix A)
- Be willing to undergo a core or excisional biopsy of a bone metastasis prior to study drug initiation for tumor tissue. *Newly-obtained is defined as a specimen obtained up to 12 weeks (84 days) prior to initiation of treatment on Day 1. Bone biopsy can have been done prior to screening; archival specimens of bone metastasis are permitted if done for other purpose and available.*
 - If biopsy is non-diagnostic, patient must undergo repeat biopsy as proof of tumor tissue by pathology review. Proof of tumor specimen is required for eligibility. If 2nd biopsy is non-diagnostic, the patient may enroll as good faith effort.
- Be willing to undergo a second core or excisional biopsy of a bone metastasis on therapy (approximately after 8 weeks of study therapy or after 2 doses of radium-223 if delays have occurred).
- Demonstrate adequate organ function as defined in the Table below, all screening labs for eligibility should be performed within 42 days prior to treatment initiation.

System	Laboratory Value
Hematological	
Absolute neutrophil count (ANC)	≥1,500 /mcL
Platelets	≥100,000 / mcL
Hemoglobin	≥ 9 g/dL or ≥ 5.6 mmol/L; transfusions permitted
Renal	
Serum creatinine OR	≤1.5 X institutional upper limit of normal (ULN) OR
Measured or calculated ^a creatinine	
clearance	\geq 30 mL/min for subject with creatinine levels > 1.5 X
(GFR can also be used in place of	institutional ULN
creatinine or CrCl)	
Hepatic	
Serum total bilirubin	\leq 1.5 X institutional ULN OR
	Direct bilirubin \leq institutional ULN for subjects with total
	bilirubin levels > 1.5 institutional ULN
AST (SGOT) and ALT (SGPT)	\leq 2.5 X institutional ULN
Albumin	$\geq 2.5 \text{ mg/dL}$
Coagulation	
International Normalized Ratio (INR) or	≤1.5 X institutional ULN unless subject is receiving
Prothrombin Time (PT)	anticoagulant therapy as long as PT or PTT is within therapeutic
	range of intended use of anticoagulants
Activated Partial Thromboplastin Time	≤1.5 X institutional ULN unless subject is receiving
(aPTT)	anticoagulant therapy as long as PT or PTT is within therapeutic
(41 1 1)	range of intended use of anticoagulants
^a Creatinine clearance should be calculated	per institutional standard.

Table 2: Adequate Organ Function Laboratory Values

• The effects of radium-223 and pembrolizumab on the developing human fetus are unknown. For this reason, men must agree to use adequate contraception. Specifically, they must agree to use a condom (even men with vasectomies) and another effective method of birth control if he is having sex with a woman of childbearing potential or agree to use a condom if he is having sex with a woman who is pregnant while on study drug and for 120 days (4 months) following the

last dose of study drug. They must also agree not to donate sperm during the study and for 4 months after receiving the last dose of study drug.

• Ability to understand and the willingness to sign a written informed consent document.

3.3 Exclusion Criteria

- Pathology consistent with majority of specimen having small cell carcinoma of the prostate (prostate cancer with other neuroendocrine features is acceptable).
- Prior treatment with radium-223
- Prior treatment with a PD-1, PD-L1, or PD-L2 blocking therapy
- Evidence of nodal disease greater than or equal to 15 mm in short axis as these findings are concerning for metastases that would not be targeted with radium-223 alone (Arm B). However, lymph nodes with short axis measurements between 1.5-3cm that have not enlarged more than 5mm (to account for reader variability) over the last 6 months and which are not inducing symptoms, causing obstruction, or in the opinion of the investigator pose a risk of impending obstruction of any structures, will be allowed.
- Pulmonary nodules > 10 mm
 - Pulmonary nodules > 10mm that have been stable for >6 months and are not clearly metastatic disease per the treating investigator are permitted
- Soft tissue components of bone metastases ≥ 1.0 cm in longest axis
 - Soft tissue components of bone metastases < 1.0 cm that have been stable for >6 months (must not have enlarged > 5mm) are permitted
- Soft tissue lesions ≥ 1.0 cm in longest axis
 - Soft tissue lesions < 1.0 cm that have been stable for > 6 months (must not have enlarged > 5mm) are permitted.
- If present, primary disease in the prostate must be stable for > 6 months (defined as no growth > 5mm)
- Evidence of local recurrence in the prostate bed
- Evidence of liver metastases or visceral disease
- Has a diagnosis of immunodeficiency
- Patients requiring systemic steroid therapy with >10mg prednisone or its equivalent daily. Patients receiving systemic steroid therapy for non-autoimmune processes (e.g., COPD, adrenal replacement therapy) are permitted if on stable dose and asymptomatic.
- Has a known history of active TB (Bacillus Tuberculosis)
- Has had a prior anti-cancer monoclonal antibody (mAb) within 4 weeks prior to study Day 1 or who has not recovered (i.e., ≤ Grade 1 or at baseline) from adverse events due to agents administered more than 4 weeks earlier.
- Has had prior systemic therapy (exception: GnRH agonist or antagonist) or radiation therapy for prostate cancer within 2 weeks prior to study Day 1. There must be at least a 2 week washout period from last dose of any prior systemic or radiation therapy for prostate cancer prior to Day 1 of study treatment (including

nonsteroidal antiandrogens). Screening may commence during this washout window.

- Any patient who has not recovered (i.e., ≤ Grade 1 or at baseline) from adverse events or complications due to a previously administered systemic agent, radiation therapy, or major surgery.
 - Exceptions:
 - Subjects with ≤ Grade 2 neuropathy, hot flashes, or hypertension may qualify for the study if all other eligibility criteria met.
 - Other toxicity or complications that are deemed by the treating investigator as not clinically significant (e.g., urinary incontinence from past prostatectomy, peripheral edema from past taxane therapy)
- Diethylstilbestrol, estrogens, saw palmetto, or other preparations that are known to have possible endocrine effects on prostate cancer that have been started within the past 8 weeks, as they may affect PSA levels or response. These are allowed if the patient has been on a stable dose for at least 8 weeks prior to C1D1.
- Receiving other investigational agents
- History of allergic reactions to compounds with similar biologic or chemical composition to pembrolizumab or radium-223
- Has a known additional malignancy that is progressing or requires active treatment. Exceptions include basal cell carcinoma of the skin or squamous cell carcinoma of the skin that is planned for curative therapy.
- Has known active central nervous system (CNS) metastases and/or carcinomatous meningitis. Subjects with previously treated brain metastases may participate provided they are stable (without evidence of progression by imaging for at least four weeks prior to the first dose of trial treatment and any neurologic symptoms have returned to baseline), have no evidence of new or enlarging brain metastases, and are not using steroids for at least 7 days prior to trial treatment. This exception does not include carcinomatous meningitis, which is excluded regardless of clinical stability.
- Has active autoimmune disease that has required systemic treatment in the past 2 years (i.e. with use of disease modifying agents, corticosteroids or immunosuppressive drugs). Replacement therapy (e.g., thyroxine, insulin, or physiologic corticosteroid replacement therapy for adrenal or pituitary insufficiency, etc.) is not considered a form of systemic treatment and is allowed.
- Has known history of, or any evidence of active, non-infectious pneumonitis. A history of radiation pneumonitis which is asymptomatic with no signs of active process is allowed.
- Has a history or current evidence of any condition, therapy, or laboratory abnormality that might confound the results of the trial, interfere with the subject's participation for the full duration of the trial, or is not in the best interest of the subject to participate, in the opinion of the treating investigator.
- Has known psychiatric or substance abuse disorders that would interfere with cooperation with the requirements of the trial.
- Has a known history of Human Immunodeficiency Virus (HIV) (HIV 1/2 antibodies). HIV-positive participants on combination antiretroviral therapy are

ineligible because of the potential for pharmacokinetic interactions with pembrolizumab. In addition, these participants are at increased risk of lethal infections when treated with marrow-suppressive therapy. Appropriate studies will be undertaken in participants receiving combination antiretroviral therapy when indicated.

- Has known active Hepatitis B (e.g., HBsAg reactive) or Hepatitis C (e.g., HCV RNA is detected).
- Has received a live vaccine within 30 days of planned start of study therapy. Note: Seasonal influenza vaccines for injection are generally inactivated flu vaccines and are allowed; however intranasal influenza vaccines (e.g., Flu-Mist®) are live attenuated vaccines, and are not allowed.
- Uncontrolled intercurrent illness including, but not limited to, ongoing or active infection, severe or unstable angina, myocardial infarction, symptomatic congestive heart failure (defined as New York Heart Association Grade II or greater), arterial or venous thromboembolic events (e.g., pulmonary embolism, cerebrovascular accident including transient ischemic attacks) or clinically significant ventricular arrhythmias within 6 months prior to randomization; or significant vascular disease (e.g., aortic aneurysm, aortic dissection), symptomatic peripheral vascular disease
- Evidence of QTc prolongation as defined as QTcF > 470 ms (per Fridericia's formula)
- Inability to comply with study and/or follow-up procedures

3.4 Inclusion of Women and Minorities

Men of all races and ethnic groups are eligible for this trial.

Women are not eligible for this trial as they do not have prostates and as such do not get prostate cancer.

4. REGISTRATION PROCEDURES

4.1 General Guidelines for DF/HCC and DF/PCC Institutions

Institutions will register eligible participants in the Clinical Trials Management System (CTMS) OnCore. Registrations must occur prior to the initiation of protocol therapy. Any participant not registered to the protocol before protocol therapy begins will be considered ineligible and registration will be denied.

An investigator will confirm eligibility criteria and a member of the study team will complete the protocol-specific eligibility checklist.

Following registration, participants may begin protocol therapy. Issues that would cause treatment delays should be discussed with the Overall Principal Investigator (PI). If a participant does not receive protocol therapy following registration, the participant's

registration on the study must be canceled. Registration cancellations must be made in OnCore as soon as possible.

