5. TREATMENT PLAN

5.1 Treatment Regimen

Following registration, participants will be randomized in a 2:1 ratio to either Arm A: a combination of Radium-223 and pembrolizumab or Arm B: Radium-223 alone.

Patients will be stratified based on:

- Baseline alkaline phosphatase <220 or ≥ 220
- Volume of bone metastases (high: ≥ 4 bone metastases including one beyond the axial skeleton vs. low: <4 bone metastases)
 Based on CHAARTED (ECOG 3805) criteria²⁴

Given the varied dosing of the two agents, we will refer to weeks on study instead of cycles.

Radium-223 55kBq/kg (1.49 μ Ci)/kg will be administered intravenously (IV) slowly over 1 minute every 4 weeks for a maximum of 6 doses. Weight used for dosing should be based on institutional standards. Radium-223 will be administered in the nuclear medicine suite at DFCI and at the corresponding department for participating investigational sites.

Pembrolizumab will be given only to patients randomized to the investigational arm (Arm A). Pembrolizumab will be given at a dose of 200mg intravenously every 3 weeks. It will be administered in the Yawkey Infusion Center at DFCI and at the corresponding department for participating investigational sites.

Treatment with both agents will be administered on an outpatient basis. Reported adverse events and potential risks are described in Section 7. No investigational or commercial agents or therapies other than those described below may be administered with the intent to treat the participant's prostate cancer.

No dose modifications will be made for either agent. If study agents are held for more than 12 weeks (for pembrolizumab) or 8 weeks (for Radium-223) due to study drug-related toxicity, the patient should be discontinued from the offending agent. Patients may continue on either agent alone if tolerating.

Agent	Premedication	Dose	Route	Schedule
Pembrolizumab	None unless	200mg	IV 30 minutes	Every 3 weeks (21 +/-3
	prior reaction;	(diluted	-5 min/+ 10	days)
	(see Table 6)	per	min	
		institution		*Should be given prior
		al		to radium on days
		guidelines		when they are given
		/package		together.
		insert)		
Radium-223	None	55kBq/kg	IV over 1	Every 4 weeks (28 +/-
		(1.49µCi)/	minute or	7 days) for 3 doses
		kg	longer per	followed by a break
			institutional	until radiologic disease
			standards	progression. Then the
				last 3 doses will be
				given every 4 weeks
				(28 +/-7 days)

Table 3: ARM A - Combination Investigational Arm

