*Lupron/GnRH agonist or antagonist should be continued unless intolerable or discontinued for other safety reasons.

**Adhering to the schedule should be encouraged, and the 7 day window should not be utilized to give pembrolizumab and radium-223 on the same day for scheduling convenience.

Order of Administration – In the combination arm, pembrolizumab should be administered prior to radium-223 on days when both are given on the same day. No minimum time is required between the administration of drugs.

Table 4: ARM B - Control Arm

Agent	Premedication	Dose	Route	Schedule
Radium-223	None	55kBq/kg	IV over 1 minute	Every 4
		(1.49µCi)/kg	or longer per	weeks (28
			institutional	+/- 7 days)
			standards	for 6 doses

*Lupron/GnRH agonist or antagonist should be continued unless intolerable or discontinued for other safety reasons.

Trial treatment should begin on the day of randomization or within 7 days after randomization.

The Pharmacy Manual contains specific instructions for the preparation of the pembrolizumab infusion fluid and administration of infusion solution (Section 8.1).

5.2 **Pre-Treatment Criteria**

5.2.1 Cycle 1, Day 1

Pre-Treatment Criteria for C1D1. D1 dosing criteria of subsequent cycles (2 and beyond) should follow Section 6 guidelines:

C1D1 labs must meet the following criteria prior to treatment but do not need to re-meet eligibility criteria:

- Absolute neutrophil count \geq 1,500/mcL
- Hemoglobin ≥10g/dL *transfusions and/or erythropoietin supplementation permitted
- Platelets $\geq 100,000/mcL$
- Total bilirubin ≤1.5x institution's upper limit of normal (unless known Gilbert's syndrome)
- AST(SGOT)/ALT(SGPT) $\leq 2.5 \times$ institutional upper limit of normal ULN
- Creatinine clearance ≥30 mL/min/1.73 m² for participants with creatinine levels above institutional ULN. (*Note: creatinine clearance should be calculated per institutional standard*)
- If screening assessments have been done within 72 hrs prior to C1D1, they may be used in lieu of repeat C1D1 assessments (e.g., labs, ECOG, exam).

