11.1.8 Evaluation of Time to Event Endpoints

Progression-Free Survival: Progression-Free Survival (PFS) is defined as the time from randomization (or registration) to the earlier of progression or death due to

any cause. Participants alive without disease progression are censored at date of last disease evaluation.

Time to Progression: Time to Progression (TTP) is defined as the time from randomization (or registration) to progression, or censored at date of last disease evaluation for those without progression reported.

Overall Survival: Overall Survival (OS) is defined as the time from randomization (or registration) to death due to any cause, or censored at date last known alive.

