13. STATISTICAL CONSIDERATIONS

13.1 Study Design/Endpoints

This is an open label phase 2 trial that randomizes 45 mCRPC patients (2:1 ratio) to radium-223 plus pembrolizumab combination therapy or to radium-223 monotherapy. The primary objective is to compare the increase in immune CD8+ and CD4+ T cell infiltration levels from baseline to 8 weeks on treatment between the two treatment arms.

Primary Endpoint:

Difference in tissue immune cell (e.g., CD4+/8+T) infiltration in the bone metastasis biopsy specimens from baseline to 8 weeks on treatments in both the combination and monotherapy arms.

Secondary Endpoints:

- Safety and Tolerability: grade 3 or higher adverse events that are considered treatment related according to NCI CTCAE (version 4.0)
- Progression-free survival (PFS): is defined as the time from the first dose of study drug to the earlier of the first documentation of definitive disease progression [as

defined by Response Evaluation Criteria in Solid Tumors (RECIST version 1.1) and PCWG2] or death due to any cause. Participants alive without disease progression are censored at date of last disease evaluation

• Overall survival as defined in 11.1.8

Exploratory Endpoints:

- Clinical-based endpoints
 - Changes in PSA
 - PSA response: defined as decline ≥50% from baseline to 12 weeks of therapy and which has been confirmed with a second PSA at ≥ 3 weeks later
 - Time to PSA progression as defined in 11.1.9
 - Time to normalization of alkaline phosphatase (if initially elevated)
 - Time to decrease in alkaline phosphatase (if initially elevated)
 - Symptomatic skeletal events (SSEs): Rate of SSEs and time to first SSE
 - Changes in osteoblastic activity on bone scan (assessed using the quantitative SPECT/CT)
 - Changes in quality of life, pain, and analgesic use, and time to introduction of analgesics
 - Immune-based endpoints
 - Quantify the CD8, CD4, and FoxP3+ CD4 (Treg) cell infiltration in the bone biopsy specimens, and to subsequently quantify the CD8/Treg and CD4/Treg ratios
 - Change in circulating T cell clonality
 - Induction of IgG antibody response
 - Changes in PD-L1 expression and co-regulation of other immune checkpoints such as TIM-3, LAG-3, and PD-L2
 - Changes in immunosuppressive cell populations and cytokines (e.g., MDSCs, Tregs, TGF-β, and iNOS)
 - Change in serum chemokines: (e.g., CXCL9, CXCL10)

- Changes in soluble PD-L1 ([name] Lab assay)
- Genomic-based endpoints

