13.12.2 Evaluation of the Primary Efficacy Endpoint

There is no primary efficacy endpoint.

Analyses of secondary efficacy endpoints will be on an intent-to-treat basis. Specifically, all eligible participants included in the study must be assessed for response/outcome to therapy, even if there are major protocol therapy deviations.

Subanalyses may then be performed on the basis of a subset of participants,

excluding those for whom major protocol deviations have been identified (e.g., early death due to other reasons, early discontinuation of treatment, major protocol violations, etc.). However, these subanalyses may not serve as the basis for drawing conclusions concerning treatment efficacy, and the reasons for excluding participants from the analysis should be clearly reported. If applicable to the endpoint, the 95% confidence intervals will be provided.

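### Sections 4.1, 13.1 and 13.6 contradict the intent-to-treat analysis of PFS and OS promised in 13.12.2; one population and one start date are needed

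*Combined protocol and SAP*

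**What the plan says.** **Registration.** Section 4.1 states: "If a participant does not receive protocol therapy following registration", the participant's "registration on the study must be canceled". It makes no distinction between patients who have been randomized and those who have not.

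**Sequence.** Section 5.1 states: "Following registration, participants will be randomized in a 2:1 ratio". It adds: "Trial treatment should begin on the day of randomization or within 7 days after randomization". The trial is open label (1.1, 13.1).

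**Start of PFS.** In the secondary endpoints of 13.1, PFS "is defined as the time from the first dose of study drug". Section 11.1.8 starts PFS at randomization, with registration as a bracketed alternative. The genomic PFS definition, also in 13.1, starts at randomization. OS in 13.1 is taken from 11.1.8, so it starts at randomization or registration.

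**Analysis set.** Section 13.12.2 states: "Analyses of secondary efficacy endpoints will be on an intent-to-treat basis". It explains that every eligible participant in the study is to be assessed, whatever the deviations from protocol therapy. Section 13.6 defines a primary analysis population of dosed patients whose bone biopsies were assessed at both baseline and week 8. It applies that population to the primary, secondary and exploratory endpoints alike.

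**The concern.** Intent-to-treat means that everyone randomized is counted, in the arm assigned, from randomization. Three parts of this plan work against that. The cancellation rule acts after the arm is known. The 13.1 definition of PFS gives an undosed patient no starting point. The 13.6 population drops patients for lack of a second biopsy, which is itself a post-randomization event.

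Loss before dosing is plausible. Arm B is radium-223 alone, which is commercially available (8.2.5) and given on its standard schedule (Study Calendar, footnote J), so a patient allocated to it can obtain the same drug outside the trial. A patient can also be eligible and randomized, yet not meet the day-1 laboratory criteria of 5.2.1. If such losses differ between arms, dropping the patients biases the comparison of PFS and OS, the two named secondary efficacy endpoints. Even without bias, two analysts following this document could report different denominators and different PFS times.

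**Working it through.** There is no stated figure for the intent-to-treat analysis itself, so the check is mainly a comparison of the text. The arithmetic sets the size.

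**1. Can a randomized patient be cancelled?** The order is registration (4.1), then randomization (5.1), then treatment 0 to 7 days later (5.1). The rule in 4.1 depends only on not receiving therapy. A patient who is randomized, learns the arm and is never dosed therefore falls under it.

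**2. Does such a patient have a start date?**

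| Endpoint | Source | Start | Undosed patient |
|---|---|---|---|
| PFS | 13.1, secondary | first dose | none |
| PFS | 11.1.8 | randomization or registration | exists |
| PFS | 13.1, genomic | randomization | exists |
| OS | 13.1, via 11.1.8 | randomization or registration | exists |

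The missing start date thus affects PFS under one of its definitions, and does not affect OS. A smaller slip does reach OS: 13.8 counts its 6- and 12-month Kaplan-Meier estimates from treatment initiation.

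**3. How far apart are the start dates for dosed patients?** At most 7 days: 7 / 30.44 = 0.23 months. As a yardstick only, 0.23 / 6 = 3.8% of the 6-month median PFS that 13.11 assumes for patients without a DNA repair mutation.

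**4. Is follow-up provided?** Section 5.5 and footnote Q of the Study Calendar tie follow-up to removal from therapy and end it at death or two years from stopping treatment. An undosed patient has no such treatment dates, so no schedule applies.

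**5. What does 13.6 remove?** The plan's own figure reproduces: 36 / (1 - 0.20) = 45 (13.4). If the 20% allowance is used in full, 45 - 36 = 9 patients are outside the 13.6 population, leaving 24 in Arm A and 12 in Arm B. A patient who dies before the week-8 biopsy cannot be in that population, so an early death would be missing from OS.

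**6. What does each cancelled patient cost?** Planned arms are 30 and 15 (2:1 of 45).
- Arm B: 1 / 15 = 6.7% per patient.
- Arm A: 1 / 30 = 3.3% per patient.
- Overall, assuming 1 to 5 cancellations: 1 / 45 = 2.2% (44 left) to 5 / 45 = 11.1% (40 left).

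The range 1 to 5 is an assumption; the documents give no number.

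**7. Is the primary test affected?** No. It needs paired biopsies, which an undosed patient could not supply, and 13.4 already allows for 20% loss. For PFS and OS by arm, 13.8 specifies Kaplan-Meier curves, medians and confidence intervals, with no between-arm test.

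**The case against.** The strongest reply is that 4.1 is an instruction for the registration system and not an analysis rule. Nowhere is it said that cancellation ends follow-up or takes the patient out of the analysis. Not being dosed is not among the off-study criteria in 5.6. Cancellations are entered in OnCore, so they are on record. Section 4.2 also makes an institutional SOP on registration mandatory; it may deal with cancellation after randomization, and it cannot be seen here. The start-date difference applies to both arms and is no larger than the 7-day window around each 12-weekly scan. Finally, the efficacy objective is only preliminary and the estimates are descriptive.

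Much of this stands, and it rules out two stronger readings.

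- A reader might infer that an intent-to-treat analysis of PFS and OS cannot be carried out at all. The documents do not support that. OS already starts at randomization or registration, PFS does too under 11.1.8, and the analysis is feasible if randomized patients are kept and followed.
- A reader might infer that a definite share of Arm B, say 10 to 20%, will vanish without trace. No departure rate appears in the documents, and cancellations are recorded.

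The reply does not remove the contradiction. Section 13.12.2 covers those in the study, and whether a cancelled patient is in the study is left open. No follow-up is scheduled for such a patient. The 13.6 restriction is an explicit analysis rule that conflicts directly with 13.12.2, and the reply does not touch it.

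**Conclusion.** The plan is wrong as written: 4.1, the PFS definition in 13.1 and the population in 13.6 cannot all stand beside the intent-to-treat statement in 13.12.2. The consequence is limited to the descriptive PFS and OS estimates.

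Of the three conflicts, 13.6 is the only one that the plan's own figures can size: about 9 of 45 patients if the 20% allowance is fully used and every such patient lacks a paired biopsy. The cancellation rule has an unknown effect, because the number of undosed patients is not given, and with a control arm of 15 a single patient matters. The start-date conflict is negligible for dosed patients and matters mainly because, under 13.1, an undosed patient has no PFS time. That selective loss from Arm B would occur is plausible in an open-label trial, but it is an assumption.

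**What to change.** - **4.1:** limit cancellation to registrations withdrawn before randomization. Alternatively, state that cancellation removes a randomized patient neither from follow-up nor from the PFS and OS analysis set. Check the wording against the registration SOP named in 4.2.
- **13.1 and 11.1.8:** start PFS at randomization in 13.1, and delete the bracketed mention of registration in 11.1.8 so that PFS and OS share one start date. Count the 6- and 12-month estimates in 13.8 from the same date.
- **13.6:** restrict the paired-biopsy population to the biopsy-based endpoints, and analyse PFS and OS in all randomized patients by assigned arm.
- **5.5:** follow undosed randomized patients for survival, with the schedule counted from randomization.

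The cost is wording in a few sections and survival follow-up of what should be a small number of patients. No sample size, treatment or primary analysis changes.
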